A recent case report describes multiple episodes of severe hypoglycemia experienced by a 51 year old Type-I diabetic after the onset of varenicline treatment (Kristensen et al., 2008). The discontinuation of varenicline resolved any further hypoglycemic episodes. Thus, it is possible that diagnosed/undiagnosed diabetics may experience severe hypoglycemic episodes while taking varenicline. In the consent, severe hypoglycemic events will be noted as a potential side effect.

A list of treatment-emergent adverse events reported by patients during all clinical trials involving varenicline indicates that cardiac issues (e.g., arrhythmia, myocardial infarct) occurred infrequently (Pfizer insert). Given that cigarette smoking has a negative impact on the heart and the potential for cardiac side effects, in the consent cardiac disorders are noted as a potential side effect.

Risk Minimization. Only individuals who meet certain medical history criteria will be recruited into the study. Participants with a history of heart problems, diabetes, or abnormal renal functions will not be included in the present study. Doses will be titrated to reduce the severity/incidence of side effects. The daily dose of varenicline may be reduced (on a case-by-case basis) to alleviate side effects such as nausea. We have excluded individuals with current or past major psychiatric illness, and will closely monitor potential psychiatric symptoms, depression, and suicidal ideation as part of the clinical monitoring plan. The monitoring plan (see Section 8 Subject Monitoring) consists of weekly in-person assessments at NIDA-IRP during 12 week treatment visits. Drug administration procedures will be terminated immediately upon participant request. In the event of a severe side effect such as a hypoglycemic event, myocardial infarction/arrhythmia, or increase in suicidal ideation, participants will be advised to immediately discontinue study pill administration. If seeking medical care, participants will be instructed to notify their physician or medical care providers of the fact that they are taking varenicline.

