Research Database (N = 80, 660) found no significant difference between varenicline and nicotine replacement therapy in reported incidents of fatal and non-fatal self-harm (0.16% vs 0.22%), suicidal ideation (0.05% vs 0.05%) or initiation of anti-depressant use (3.18% vs 3.62%) (Gunnell, Irvine, Wise, Davies, & Martin, 2009). Nevertheless, to help mitigate potential risks related to changes in mood, behavior, or suicidal ideation and to assess for all side effects, a clinical monitoring plan involving weekly in-person assessments during the 12-week treatment period will be implemented. During their initial treatment interview (the day they set their quit date) or during their final pretreatment visit they will briefly meet with the study MAI or the designated NIDA-IRP physician in the MAI's absence who will distribute a 2 weeks supply of varenicline and carefully describe the medication, prescribed dosing schedule and possible side-effects. Participants will also receive a set of take-home instructions and information sheet (see Appendix 8). During each weekly visit across the entire 12-week treatment participants will receive a nurse assessment to assess vital signs and complete a series of questionnaires (see Appendix 4). During their counseling session the therapist will administer a semi-structured interview (see Appendix 7) to assess for psychiatric and physical symptoms. If participants are unable to attend their weekly counseling session in person, study therapists, LI or study clinician will conduct telephone assessments to monitor for changes in physical and psychiatric symptoms (administering the varenicline toleration assessment, Appendix 7). The same assessment will also be conducted each week for the first two weeks after their last Varenicline dose. At any time during the study, endorsement of one or more items listed in Appendix 7 will be referred to the study MAI or a NIDA-IRP clinician in the MAIs absence to who will determine if the endorsement requires further action. Participants with suicidal ideations, atypical changes in behavior, or experiencing clinically significant or difficult to tolerate side effects may be provided with a referral, instructed to stop taking the study pills, and/or be withdrawn from the study.

Date: March 2, 2022

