9.2. Criteria to be used

Participants who experience a serious expected or unexpected adverse event (i.e., require hospitalization, experience significant disability/incapacitation, death, or have a life-threatening reaction) with likely or greater relationship to the experimental procedures will be excluded from any further participation. Participants may also be withdrawn from the study should they experience a serious allergic reaction to the nicotine or placebo patch adhesive. Should participants fail to comply with the 36 hr smoking abstinence, they will be asked to reschedule their scanning visit and recomplete the 36 hr abstinence. If they do not wish to reschedule, they will be withdrawn from the study.

Date: March 2, 2022

No specific data on the toxic dose of varenicline appear to be available. The toxic dose of varenicline may be dependent on previous experience with nicotine. Specifically, smokers are able to tolerate higher single-doses of varenicline than non-smokers (Faessel et al., 2006a). Varenicline is well tolerated in single doses up to 3mg (Faessel et al., 2006a) and in multiple doses up to and including 2mg daily (Faessel et al., 2006b) with nausea and vomiting being limiting factors. Participants may be discontinued from varenicline treatment and offered alternative treatment (i.e., nicotine replacement therapy) depending on the severity of varenicline related side effects. The daily dose of varenicline may be reduced (on a case-by-case basis) to alleviate side effects and increase retention rates if necessary.

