Appendix 7: Varenicline Toleration Assessment

After participants start varenicline, a masters level therapist, LI, or study clinician will conduct a semi-structured interview to assess toleration of varenicline. The assessment will be conducted weekly, either in person or via phone, while participants are taking varenicline, and for two weeks after their last dose. The therapist will be extensively trained by the MAI on question administration. If the interview reveals a possibility of significant side effects, the participant will be put in contact with the MAI for further evaluation. The MAI will decide whether study pill administration needs to be discontinued and other action taken based on the severity of the symptoms.

- 1) Since we last spoke or met, how have you been feeling? (open-ended question)
- 2) Have you noticed any physical side effects [or, a change in the severity of any physical side effects], such as nausea, vomiting, dizziness, or headache? Anything else?
- 3) Have you noticed a change in behavior that would be considered out of the ordinary for you?
 - 4) Do you feel more restless, wound-up, or agitated than usual?
 - 5) Do you feel more irritable or cranky than usual?
- 6) Have you noticed an increase in feelings of depression, such as sadness, hopelessness, helplessness or worthlessness?
- 8) Have you had thoughts of violence towards others? ...acted aggressively towards someone?
- 7) Have you had thoughts of death? ...wished you were dead? ...had thoughts of killing yourself?

Participants will also be reminded to call if any issues should arise between assessments.

Principal Investigator: [name].

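### Section 8.3 promises immediate advice to stop varenicline if suicidal ideation increases, but section 9.1 and Appendix 7 make stopping discretionary and say nothing about the next dose

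*Combined protocol and SAP*

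**What the plan says.** Four places in the combined protocol and SAP bear on this.

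- **Section 8.3 (Risk Minimization)** names a rise in suicidal ideation as one example of a severe side effect, alongside hypoglycemic and cardiac events. The response is fixed: "increase in suicidal ideation, participants will be advised to immediately discontinue study pill administration".
- **Section 9.1** first sends any endorsed Appendix 7 item to the MAI, or to another institute clinician if the MAI is absent, "who will determine if the endorsement requires further action". It then states: "Participants with suicidal ideations, atypical changes in behavior, or experiencing clinically significant or difficult to tolerate side effects may be provided with a referral". The same sentence lists two further options, equally discretionary, under which such a participant could be "instructed to stop taking the study pills, and/or be withdrawn from the study".
- **Appendix 7**, the weekly toleration interview, asks directly about thoughts of death, wishing to be dead and thoughts of suicide. If significant side effects seem possible, "the participant will be put in contact with the MAI for further evaluation". Then: "The MAI will decide whether study pill administration needs to be discontinued and other action taken based on the severity of the symptoms".
- **Appendix 8**, the participant's take-home sheet, says to stop the pills at once and make contact for any worrisome side effect. It repeats the stop instruction for suicidal thoughts or behaviors arising with a sudden or drastic change in mood or behavior.

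**The concern.** The same event gets a mandatory answer in one part of the protocol and a discretionary one in two others. Section 8.3 sets the policy and Appendix 8 gives it to participants. The sections that describe what happens when an interviewer hears about ideation, 9.1 and Appendix 7, do not repeat it. Neither says what the interviewer should tell the participant about the next tablet while the clinician is being reached.

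Patient safety is at stake, in one specific situation. Appendix 7 asks directly, so it can find people who have not raised the matter themselves or acted on the take-home sheet. For them the interviewer's advice is the remaining written safeguard, and the guide the interviewer holds does not contain it.

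**Working it through.** The plan has no figure of its own to reproduce here. The check is a comparison of texts, followed by a short calculation of how often the situation might arise.

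**1. Compare the rules for a participant who tells the interviewer of new suicidal ideation.**

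- Section 8.3: advise stopping now. No discretion.
- Section 9.1: referral to a clinician is required. After that, referral, stopping and withdrawal are all optional.
- Appendix 7: contact with the MAI is required where significant side effects are possible. Stopping depends on the MAI's view of severity.
- Appendix 8: the participant should already have stopped.

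Suppose the participant is referred and dosing continues. That conduct complies with 9.1 and is open to the MAI under Appendix 7, but it breaches 8.3. This is a conflict between stated rules, not just missing detail.

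**2. Does new ideation count as an increase?** Exclusion criterion 6 in section 3.3 rules out anyone with current suicidal ideation. Ideation first reported on varenicline is therefore a rise from the entry state, and the 8.3 trigger is met.

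**3. How soon is the next dose?** Section 4.4(v) gives varenicline twice daily from day 4, with doses at least 8 hours apart. The next dose can fall on the same day as the interview. Neither 9.1 nor Appendix 7 requires the clinician to be reached before the interview ends.

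**4. How often might any ideation occur?** The only rate is from the cohort study cited in 9.1, comparing varenicline with nicotine replacement: "suicidal ideation (0.05% vs 0.05" percent). Section 11.5 expects 120 treatment-seeking enrollees and 85 completers. Assume the number who start varenicline lies between these. With p = 0.0005:

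- Expected cases, n × p: 85 × 0.0005 = 0.0425; 120 × 0.0005 = 0.06.
- Chance of at least one, 1 − (1 − p)^n: 1 − 0.9995^85 = 0.042; 1 − 0.9995^120 = 0.058.

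This gives 0.04 to 0.06 expected cases, or about a 4% to 6% chance of at least one.

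**5. What that number leaves out.** The gap has an effect only if a case occurs, the participant has not already acted on Appendix 8, the first disclosure is at interview, and no clinician is reached before the next dose. The documents give no probability for the last three, so the chance of the gap mattering cannot be computed. If the borrowed rate applied, it could be no larger than the 4% to 6%.

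**The case against.** The strongest reply is that the texts can be read together: 8.3 applies to severe side effects, while 9.1 and Appendix 7 say who judges severity. This fails on the wording. Section 8.3 gives a rise in suicidal ideation as an instance of a severe side effect, so severity is not left open for that event.

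A second reply is that 8.3 is itself operative text, and advice to participants can only come from staff. That is right. A reader might infer that interviewers are never told the 8.3 rule, but the documents do not support that. The therapist manual and the MAI's training of interviewers are mentioned but not included. What can be said is that the written interview guide and 9.1 omit the rule.

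A third reply is that the safeguards are substantial, and this stands. Referral under 9.1 is mandatory, the MAI or a designated clinician is on call by beeper or phone, nurses can be reached 24 hours a day, interviewers are trained and supervised, and Appendix 8 already tells participants to stop. It would be wrong to conclude that participants have no interim dosing instruction. They have one, and the weakness is confined to those who have not acted on it.

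A reader might also count section 9.2 as part of the conflict, because it says "Participants may be discontinued from varenicline treatment and offered alternative treatment (i.e., nicotine replacement therapy) depending on the severity of varenicline related side effects". It is not. That sentence concerns varenicline side effects generally, follows text on tolerated doses, nausea and vomiting, and does not mention ideation.

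Finally, the 4% to 6% might be taken as the risk created by the gap. It is only the chance of any ideation case, at a rate from a general-practice database. This trial excludes current psychiatric illness and ideation, which could lower the true rate, and asks about ideation every week, which could raise detection.

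**Conclusion.** The inconsistency is real: 8.3 and Appendix 8 call for stopping at once, while 9.1 and Appendix 7 leave stopping to discretion and are silent on the next dose. Confidence is high on the wording. The practical consequence is narrow and cannot be quantified from the documents. The illustrative 4% to 6% rests on the cited 0.05% applying here and on 85 to 120 people starting varenicline. The event is rare but potentially grave, several safeguards would have to fail together, and the sponsor has already chosen the rule. This is a cheap improvement, not a fundamental flaw.

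**What to change.** Carry the 8.3 rule into the two texts that lack it.

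1. **Section 9.1.** Take new or increased suicidal ideation out of the discretionary list. State that the participant is advised to stop the pills immediately, followed by review by the MAI or covering clinician. Keep the discretion for the other effects.
2. **Appendix 7.** State that if a participant reports thoughts of suicide, or other new or worse suicidal ideation, the interviewer advises holding the pills and connects the participant, during the same contact, with the MAI or covering clinician. That clinician decides on restart, discontinuation, referral or withdrawal. Leave thoughts of death alone with MAI triage, and state explicitly which branch a wish to be dead falls in, so that interviewers need not decide.

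Section 9.2 needs no change. The cost is one amendment and a short interviewer briefing, with no added visits or staff. The downside is a few missed doses for a participant whose ideation proves unrelated to the drug.

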8.4. Smoking abstinence/nicotine deprivation

The 36 hr nicotine deprivation is expected to produce acute nicotine withdrawal symptoms, and hence some degree of discomfort. According to the DSM-IV (APA, 1994) acute nicotine withdrawal is associated with the following symptoms:

- dysphoric or depressed mood
- insomnia
- irritability, frustration, or anger
- anxiety
- difficulty concentrating
- restlessness
- decreased heart rate
- increased appetite

As our primary interest in the current protocol is the neurobiological mechanisms underlying acute nicotine withdrawal symptoms, no specific efforts will be made to minimize the discomfort associated with these

Principal Investigator: [name].

symptoms during the participant's abstinence period or scanning session. However, participants will be fully aware that their participation is voluntary and that they can withdraw from the study at any time, including during the abstinence period or scanning session.

Date: March 2, 2022

8.5. Blood draw

AEs related to blood draw may include:

- Minor Skin irritation
- Pain/Discomfort
- Scarring
- Syncope
- Weakness
- light-headedness
- Bleeding
- Swelling at draw site
- Infection

Risk Minimization. Blood draws will only be performed by experienced medical or nursing staff. Risk of Infection is minimized by the use of sterile blood drawing procedures.

8.6. Intravenous Catheter

Possible side effects of intravenous catheter insertion might include acute pain, infection, phlebitis, lightheadedness/fainting or bruising.

Risk Minimization. Intravenous catheter insertion and blood draw will only be performed by experienced medical or nursing staff.

8.7. MRI Scanning.

When used on appropriately qualified individuals, MRI presents minimal risk as long as technical scan parameters remain within FDA guidelines. There is no exposure to x-rays or radioactivity. The radio waves used have produced burns (most of these minor) in about one in a million exams. The magnet may move metal implants in the body, the motion of which could be painful and harmful. Metal implants may also cause burns from the radio frequency energy used. While inside the magnet, subjects may experience an acute panic attack due to claustrophobia. Subjects may also experience mild, remittable discomfort from lying in the scanner.

Risk Minimization. To ensure adherence to FDA guidelines for MRI, a trained MRI operator who has been instructed in these guidelines performs all machine manipulations. Other preventative measures include assuring that all equipment to be used during imaging sessions is MR compatible, that participants are familiar with the MRI environment (using the mock scanner), and that participants are aware of how to signal the MR operator if they need to do so during the session. Furthermore, participants are screened prior to each MRI session for any MR contraindications, including metal implants, pregnancy, fear of small, enclosed spaces, and inability to lie still for prolonged periods of time.

Principal Investigator: [name].

8.8. EEG Recording.

When recording EEG an elastic cap containing electrodes is placed on the participants head. During preparation conductive gel is inserted into each electrode cup and worked into place using the blunt end of a cotton swab. Subjects may experience mild scalp irritation during the preparation process. Extended periods of time (typically > 6hrs) wearing the EEG cap may produce tension headaches. Some people may experience tension headaches after shorter periods of time, particularly if the cap fits tightly around their heads. Participants will need to wash the conductive gel from their hair at the end of the recording session.

Date: March 2, 2022

Risk Minimization. All EEG preparation was conducted by [name], who has extensive experience conducting EEG research. Participants will not wear the EEG cap for more than 6 hrs (typically no more than 3 hours) and can ask to have it removed at any time if too uncomfortable. Participants will be informed of the EEG clean-up process before enrolling.

8.9. Physiological monitoring.

The tape (or electrodes) used to attach the wires may cause minor skin rash.

Risk minimization. If this happens, a decision will be made by the MAI about whether the participant should complete this part of the experiment.

8.10. Tasks completed inside and outside of the scanner.

Participants may find the tasks that they are asked to perform during, before and after scanning sessions boring, difficult, and/or frustrating.

Risk Minimization. In order to reduce discomforts associated with performing the emotional and cognitive tasks, scanning sessions and task sessions outside of the scanner are organized in such a way that participants will not perform tasks for extended periods of time and will be given a chance to rest between tasks. In addition, the tasks are designed to make performance neither too difficult nor too easy. Ideally, individual adjustments of task difficulty enable participants to remain actively engaged in the task. Participants receive extensive training before the actual experimental task begins.

8.11. Presentation of smoking-related pictures.

This protocol includes several procedures which involve the presentation of smoking-related pictures which are likely to induce or increase craving/urge to smoke and may also cause some mild distress.

Risk minimization. The craving/mild distress elicited by these procedures is a primary outcome measure of interest and central to the manipulation. There will thus be no effort to minimize the craving/mild distress experienced by participants. However, participants will be made fully aware during the consent process that they have the right to discontinue this procedure without consequence at any time.

8.12. Self-report characterization and state measures

Some questions asked may be perceived as embarrassing or may cause anxiety or distress. Nevertheless, such reactions are expected to be temporary and to rapidly dissipate spontaneously.

Risk Minimization. Participants will be advised prior to completing these measures that they may refuse to answer any questions that cause them discomfort. Furthermore, any participant who experiences anxiety or distress as a result of these assessments will be able to discuss it with a NIDA IRP mental-health professional.

Date: March 2, 2022

Principal Investigator: [name].

8.13. Electric shock.

Electric shock as administered in the proposed study poses minimal risk to participants and some discomfort which is similar to that of having a tight rubber band snapped against the skin.

Risk Minimization. Risk of discomfort is minimized by employing the shock workup procedure described in section 4.4 Study Procedures. During the consent process and again after the shock workup procedure, participants are explicitly informed of their right to discontinue the procedure without consequence at any point.

8.14. Electric shock within the MRI scanner.

Introduction of electrical wires that are connected to the participant in the strong magnetic field of the scanner may constitute an additional risk. The main risk associated with administering shocks is the introduction of electrode wires directly in the RF (radiofrequency) field of the magnet. To minimize this risk, wires will not be exposed to the radiofrequencies induced in the RF head coil. The shock stimulator equipment will be outside the magnetic area, and a plastic and copper cable is taken through the wall for connection to the participant electrodes. To eliminate the possibility that electrode wires will enter the RF-field from participant movements, shock electrodes will be attached to either the foot or ankle region. Area between the wires will be minimized by twisting the wires together, and coiling of the wires will be prevented by inspection prior to each session (i.e., wires run without loops). MRI compatibility of all devices/wires entering the magnetic field of the scanner is determined by [name], a staff scientist here at NIDA-IRP. [name] has a doctorate in Experimental Plasma Physics and has extensive experience in the acquisition and analysis MRI data and in the development of MRI compatible procedures.

8.15. Acoustic Noise.

Some subjects may experience temporary, reversible shifts in hearing threshold after MRI.

Risk Minimization. The sound generated by an MR system usually consists of a series of repetitive pulses. Acoustic noise is a result of the mechanical vibration produced by the gradient coils when the large currents are applied to them to create time varying imaging gradient fields. The relevant safety parameters required to characterize such a noise are the peak impulse sound pressure level (L-peak) and the time integral of the A-weighted sound pressure level (Leq). In MR applications, the peak impulse sound pressure level is dependent upon the peak amplitude of the individual pulses, while the time integral of the A-weighted sound pressure level is dependent upon the continuous exposure to a series of such pulses. Based on Occupational Safety and Health Administration (OSHA, Occupational Noise Exposure – 1910.95, www.osha.gov) regulations: 1) exposure to impulsive or impact noise should not exceed 140 dB peak sound pressure level, and 2) exposure to continuous noise for 2 hours per day should not exceed 100 dB. Note that these regulations are based on employees' daily exposure to a noisy environment over their entire working career, whereas we use them here as a comparison for participants' occasional exposure to MRI scanner noise, thus making these values extremely conservative measures. Measurements within our MRI scanner (provided by Siemens, the manufacturer) indicate that the maximum noise level produced by our standard fMRI pulse sequence is 116.5 dB. Based upon our typical echo spacing, this sound is in the 3-4 kHz range.

According to the Occupational Safety and Health Administration regulations (OSHA, occupational noise exposure 1910.95, www.osha.gov):

- 1) Exposure to impulsive or impact noise should not exceed 140 dB peak sound pressure level, and
- 2) Exposure to continuous noise for 2 hours per day should not exceed 100 dB.

These guidelines are based on employees' daily exposure to a noisy environment over their entire working career, whereas we use them here as a comparison for participants' occasional exposure to MRI scanner noise.

Principal Investigator: [name].

This study consists of a series of scans ranging in length from a few seconds to about ten minutes. Rest periods of up to a few (1-5) minutes occur regularly between scans while the next scan is being set up.

Date: March 2, 2022

During fMRI experiments, MRI compatible headphones with tubes for audio input and/or earplugs with or without tubes for audio input are routinely used for hearing protection. In addition, a vacuum pillow or other padding used for head stabilization may also attenuate noise. Based on the manufactures specifications, the earplugs with and without audio tubes have noise reduction ratings of approximately 25dB and 33 dB. The headphones have a noise reduction rating of 29 dB. The vacuum pillow / padding foam provides additional noise reduction (values not available, but estimated at 5-15 dB). The noise reduction rating is a conservative measure that averages over frequencies and attempts to account for improper protection use. The mean noise attenuations at 3150 Hz, a frequency near that of our scanner, are actually 35dB, 47dB for the 2 types of earplugs and 40dB for the headphones used. Thus, the use of any two of these devices in combination reduces the noise level to levels much lower than that required by OSHA for lifetime exposure, and provides effective hearing protection for the participants. Nevertheless, some subjects may experience temporary, reversible shifts in hearing threshold after MRI.

8.16. Mock Scanner.

Potential side effects associated with the mock scanner include mild backache from having to lie still for a prolonged period of time, temporary difficulty hearing soft sounds after the exam, and being uncomfortable being in a small enclosed space.

Risk Minimization. Pre-study screening for history of back problems or claustrophobia will minimize the likelihood of side effect from mock scanning. In addition, participants will be given adequate hearing protection to minimize hearing difficulties resulting from mock scanning procedures (see Acoustic Noise section above for details).

9. Subject monitoring

